4.1 General Study Design and Plan

A multicenter, randomized open Phase IIB study to compare two epoetin alfa (HEMAX[®] PFS versus EPREX/ ERYPO[®]) is designed.

Pre-dialysis patients older than 18 years old with chronic kidney insufficiency (CKI), defined by glomerular filtration of ≥ 15 mL/ min/ 1.73 m², and < 60 mL/ min/ 1.73 m² using the Modification of Diet in Renal Disease Study (MDRD) formula, with indication for treating anemia and hemoglobin levels < 10.5 g/ dL, that had not received any previous treatment with erythropoietin stimulating agents 3 months before the study was initiated, were chosen.

Selected patients according to the inclusion and exclusion criteria were randomized in a ratio 1:1, stratified by gender to receive HEMAX[®] PFS or EPREX/ ERYPO[®] at an initial dose of 29 IU/ kg by subcutaneous route, twice a week (2000 IU, twice a week for 70 kg weight), to titrate according to the schedule detailed in Section 8.1 TREATMENTS ADMINISTERED. Patients' follow-up was carried out for the dose-titration during the first 12 weeks, followed by 12 additional weeks of maintenance with visits every 4 weeks.

4.2 Selection (Inclusion-Exclusion) Criteria

INCLUSION CRITERIA

Patients must meet all of the following inclusion criteria to be eligible for the study:

- 1) Patients between 18 and 85 years of age of both sexes.
- 2) IRC defined by the glomerular filtration rate through the MDRD formula that is ≥ 15 ml/ min and < 60 ml/ min by 1.73 m².
- 3) Anemia with indication of treatment and Hb lower than 10.5 g/ dl and greater than 7.5 g/ dl.
- 4) Patients who have both the will and the capacity to give informed consent in writing.
- 5) Women with at least 2 years of menopause or surgically sterile 6 months ago or of childbearing potential that have a negative pregnancy test during the baseline visit and are willing to receive an effective birth control method (diaphragm or prophylactic associated with a spermicide since at least 21 days before the first treatment; or intrauterine device in place for at least 3 months before the first dose of epoetin alfa: or hormonal birth control method, in pills, patch or implant, initiated at least 3 months before the first treatment).

EXCLUSION CRITERIA

Any of the following criteria exclude the patient from participating in the study:

- 1) Patient with scheduled entry to dialysis or kidney transplant in the next 6 months.
- 2) Transferrin saturation $< 20\%$.

- 3) Cause of renal failure (as the secondary ones to autoimmune diseases) that in the opinion of the physician may affect the normal development of the Protocol.
- 4) Active bleeding or history of hemorrhage that has caused significant decrease of hematocrits in the last 30 days.
- 5) Uncontrolled hypertension (≥ 160 mm Hg systolic pressure and/ or ≥ 100 mm Hg diastolic pressure with anti - hypertensive treatment).
- 6) Anemia due to another cause other than the kidney disease.
- 7) Transfusion in the last 3 months before the baseline or screening visit.
- 8) Treatment with an erythropoiesis stimulating agent in the 3 months prior to the baseline or screening visit.
- 9) Increased risk of thromboembolic disease: Previous history of arterial thromboembolism (CVA, TIA, Acute Coronary Syndrome or other) in the last 6 months or venous thrombosis in the last twelve months prior to the baseline visit; surgery in the last month prior to the baseline visit; prolonged standstill or orthopedic surgery scheduled in the next 6 months or any other factor which in the opinion of the investigator may increase the risk of thromboembolism in the patient.
- 10) Hematological disease, including myelodysplastic syndrome or a history of hematologic neoplasia or solid tumor in the last 5 years.
- 11) History of congestive heart failure.
- 12) Pregnancy or breast - feeding.
- 13) Refusal of patient to participate in the protocol or patients with a medical condition that the investigator considers significantly relevant to prevent their participation in the study.

4.3 Randomisation and Blinding

All patients were assigned to the corresponding treatment group by an electronic randomization software system, stratified by gender, and in blocks per center. The randomization system was defined in the electronic data collection system.

4.4 Study Variables

	V1 Screen	V2 Random	V3	V4	V5	V6	V7	V8	V9	V10	V11 or Final
PROCEDURES - SITE VISITS											
Study weeks	- 1	0	S2	S4	S6	S8	S10	S12	S16	S20	S24
INVESTIGATOR ACTIVITIES											
Obtain the informed consent in writing	X										
Evaluate the inclusion and exclusion	X	X									
Randomization		X									
Blood pregnancy test HCG beta subunit (only in women of childbearing potential)		X	X	X	X	X	X		X	X	
Medical history (with concomitant medication) and physical examination	X										

Blood pressure and pulse	X	X	X	X	X	X	X	X	X	X	X
Electrocardiogram	X										
Complete laboratory test (hemogram; hepatogram; blood glucose; renal function; ionogram; lipids; iron metabolism)	X							X			
Control laboratory test: hemogram			X	X	X	X	X		X	X	
Laboratory measurement of antibodies and hepcidin	X							X			X
Dosing and dose adjustment		X	X	X	X	X	X	X	X	X	
Administration of subcutaneous		X	X	X	X	X	X	X	X	X	
Delivery of medication and dosage record card		X	X	X	X	X	X	X	X	X	
Medication control and dose recording			X	X	X	X	X	X	X	X	X
AEs recording		X	X	X	X	X	X	X	X	X	X

Randomization Visit 2 (Week 0) will be scheduled a week after the baseline screening visit with a window of ± 3 days from the respective date.

The time-window for randomization visit is one week ± 3 days from screening visit.

The time-window for visits 3, 4, 5, 6, and 7 (weeks 2, 4, 6, 8 and 10) is two weeks ± 1 week. The time-window for visits 9, 10 and 11 (weeks 16, 20 and 24) is four weeks ± 1 week.

Adverse events will be recorded from the moment the patient signed the written informed consent, and they will be recorded all the study long. They will be reviewed and updated in each visit, and anytime the patient will be contacted by telephone

5 Sample Size

A total number of 120 patients (60 in each group) will allow, with 80% of power, to rule out a difference between treatment groups greater than 1g/ dl in hemoglobin increase from baseline value to the mean value of the visits between week 8 and 12.

The trial starting date was February 15th, 2017 and the first patient was included on February 21st, 2018 and the date in which the last patient reached the primary evaluation criterion was March 23rd, 2021. Since the study started, the recruiting rate was lower than that expected. Many participating centers included one single patient or no one. During the whole study, Biosidus made its best effort to support and accompany the recruitment in the centers. Furthermore, new centers were opened until a total of 16 centers in CABA and Buenos Aires Province were achieved. Besides, amendments to the protocol were performed to include a specialized center in Paraguay.

Since in March 2020, an emergency situation was decreed due to COVID-19 pandemic. On March 20th, 2020, the Argentine National Administration for Drugs, Food, and Medical Devices (ANMAT) issued a set of regulations and recommendations, in a document titled "Regulations and recommendations regarding clinical pharmacology studies during the COVID-19 pandemic", in order to preserve the activities regarding the clinical pharmacology studies, protecting the safety and welfare of the study participants. As a consequence, and according to the clauses, Biosidus S.A. designed a risk mitigation plan (Annex 14.13), that was submitted to the Study Ethics Committees and to ANMAT.

Although the recruiting was not suspended, the health situation determined a reduction in the recruitment ratio. The interim analysis according to the obtained data showed, preliminary, that the results were those expected and allowed the conclusions of this report to be valid enough statistically, though the "n" was lower than that estimated at the beginning.

Considering that the studied population is a population at risk, and that the internal analysis gave consistent results, the recruitment was ended before achieving the 120-patient-target, and finally the study enrolled 43 patients (23 in HEMAX group, and 20 in Eprex/ Erypo® group)..

Thus, the population safety was considered as a priority, and, moreover, the integrity of the results, already collected, were kept.

6 General Considerations

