16 STATISTICAL METHODOLOGY

16.1 SAMPLE SIZE JUSTIFICATION

A total N of 120 patients (60 in each group) will allow, with 80% of power, to rule out a difference between treatment groups greater than 1g/ dl in hemoglobin increase from baseline value to the mean value of the visits between week 8 and 12.

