3.2.4 Statistical Hypotheses

Treatment equivalence will be established if the difference between the two groups excludes a difference between treatment groups greater than 1g/ dl in hemoglobin increase from baseline value to the mean value of the visits between week 8 and 12 with a difference in the mean dose of epoetin alfa in these visits no greater than 20%.

The following equivalence statistical hypotheses is to be tested at a two-sided significance level of 5%:

- H0: Treatment difference in mean Hb during the primary efficacy evaluation period, between treatment arms (HEMAX PFS versus EPREX/ERYPO®), is within ± 1.0 g/dL or less.
- H1: Treatment difference in mean Hb during the primary efficacy evaluation period, between treatment arms (HEMAX PFS versus EPREX/ERYPO®), is greater than ± 1.0 g/dL.

Only when the primary endpoint achieves equivalence, statistical testing will progress to the secondary endpoints according to the stepdown procedure.

4 Study Methods

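### SAP section 5 keeps the 80% power of a 120-patient trial, calls conclusions from 43 patients statistically valid without any supporting figure, and does not describe the look cited for ending recruitment

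*SAP*

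**What the plan says.** The protocol (16.1) states: "A total N of 120 patients (60 in each group) will allow, with 80% of power, to rule out a difference between treatment groups" larger than 1 g/dl in hemoglobin increase. SAP section 5 repeats it almost word for word: "A total number of 120 patients (60 in each group) will allow, with 80% of power, to rule out a difference between treatment groups" above that margin. Neither gives an SD, an assumed true difference or a dropout allowance.

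The same SAP section then describes slow accrual ("Many participating centers included one single patient or no one"), the COVID-19 emergency and an interim analysis. It concedes that n was lower than estimated, but says that "the results were those expected and allowed the conclusions of this report to be valid enough statistically". The stopping sentence gives two reasons. One is that the patients are a population at risk. The other opens the rest of the sentence: "the internal analysis gave consistent results, the recruitment was ended before achieving the 120-patient-target, and finally the study enrolled 43 patients", 23 on HEMAX PFS and 20 on the comparator.

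The primary analysis uses the per-protocol set (SAP 8.1). That set requires the week 12 visit (6.2.1), and patients without an evaluable week 12 hemoglobin can be excluded (7.2). The only early analysis defined, in SAP 6.4 and protocol 16.4, follows the last patient's week 12 visit. SAP 3.2.4 sets an equivalence hypothesis that "is to be tested at a two-sided significance level of 5"%, makes secondary testing conditional on it, and mentions no other look.

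**The concern.** There are two gaps. First, the only power figure in the SAP belongs to a sample that was not reached. The sentence that vouches for the smaller sample offers nothing by which a reader could judge it, either for the 43 enrolled or for the per-protocol set, which may be smaller.

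Second, results seen during the trial are cited as a reason for ending it, in an open-label study, yet the SAP does not say when the look took place, on how many patients, whether by arm, who saw it or under what rule. This is the part that could affect a declared equivalence and the secondary tests that depend on it. Without that record a reader cannot tell whether the error rate is the nominal one.

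**Working it through.** **Inputs.** Margin 1 g/dl, 60 per group, 80% power (protocol 16.1, SAP 5); 23 and 20 enrolled (SAP 5); 5% level (SAP 3.2.4), which does not settle whether a 90% or a 95% CI is meant. Results are therefore given as 90% CI / 95% CI. SD and true difference are not stated, so every value used for them below is an assumption.

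**1. The plan's own figure.** The 120 cannot be reproduced without an SD. It can only be inverted. Equivalence is declared if |d| + t·s·√(1/n₁ + 1/n₂) < 1. Solving for the SD that gives 80% at 60 / 60 with true difference 0 yields 1.86 / 1.68. Other planning assumptions give other values: 1.63 / 1.45 at true difference 0.25, and 1.66 / 1.50 if 120 allowed for 20% loss (48 evaluable per group, true difference 0). These are back-solved, not predicted. The restricted baseline range, the averaging over visits and ANCOVA would tend to lower the residual SD.

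**2. The same rule at 23 and 20** (all 43 analysed, true difference 0). √(1/23 + 1/20) = 0.306 and t on 41 df is 1.683 / 2.020, so the CI half-width is 0.51 / 0.62 times the SD.

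| SD (g/dl) | Power, 90% CI | Power, 95% CI |
|---|---|---|
| 1.0 | 88% | 78% |
| 1.2 | 70% | 52% |
| 1.5 | 38% | 16% |
| back-solved 1.86 / 1.68 | 10% | 5% |

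If the plan assumed a true difference of 0.25 and that difference holds, power at 43 is 23% / 18%. Power reaches 80% only if the SD is at most 1.10 / 0.99, or 1.03 / 0.92 for an illustrative per-protocol set of 20 and 18.

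All of this concerns hemoglobin alone. Equivalence also needs a mean dose difference of at most 20% (SAP 3.2.4, 8.1), which can only lower the chance of declaring it.

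**3. Which way low power works.** Under the rule that the data must exclude a difference above 1 g/dl, a small sample makes equivalence harder to declare. The formal hypotheses in SAP 3.2.4 run the other way: H0 is that the difference lies within ±1.0. Tested in that order, a small sample makes H0 easier to retain.

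**4. Is the look the one in SAP 6.4?** That analysis follows the last patient's week 12 visit, and "the date in which the last patient reached the primary evaluation criterion was March 23rd, 2021". Enrolment would by then have been closed for about 12 weeks, so a look that informed the stop was probably a different one. This is an inference; the date of the look would settle it.

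**5. Type I error for the hemoglobin criterion.** Simulated at true difference 1.0: test at 23 / 20 and, if equivalence is not met, test again at the larger total.

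| If not met at 43 | SD 0.8–1.0 (nominal 5% / 2.5%) | Back-solved SD |
|---|---|---|
| trial ends regardless | 5.0% / 2.5% | 2.2% / 0.8% |
| continue to 60 in total | 7.2–7.3% / 3.8% | about 5.5% / 2.4% |
| continue to 120 in total | 8.4–8.5% / 4.4% | about 6.8% / 3.2% |

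The lowest power and the largest inflation need different SDs and cannot both apply.

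**6. Plausibility of continuing.** From first inclusion (21 February 2018) to 23 March 2021 is 1126 days. Less 84 days for 12 weeks leaves 1042 days, or 34.2 months. 43 / 34.2 = 1.26 patients a month, so the missing 77 would have taken about 61 more months. Continuing to 120 is an upper bound.

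**The case against.** The SAP openly says that n fell short. The trial recruited slowly throughout, ran into a pandemic in a population at risk, and could not realistically have reached 120, so it may well have ended near 43 whatever the look showed; in that case the error rate is not inflated. Section 6.4 does define an interim analysis, the term section 5 also uses, and the two could be the same if recruitment was formally closed only after the week 12 analysis. Section 5 refers to a report that may describe the look. With enrolment closed, power at 43 changes no decision, and the achieved CI width is a result for the report.

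Much of this stands. It limits the claim to what the SAP records and lowers confidence that the look was separate. It does not supply a figure behind the statement on validity, and it does not remove the analysis from the stopping sentence.

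A reader might infer more: that 43 patients are too few, that the trial was stopped because the results were favourable, or that a declared equivalence would be false. The documents support none of these. Adequacy turns on an unstated SD. The analysis is one of two reasons given, and nothing shows that the trial would otherwise have continued. Under the CI rule, low power does not make a declared equivalence false.

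**Conclusion.** The point holds as a fault of documentation that should be fixed. Confidence is high that the 80% does not apply to 43 and that the SAP offers nothing to separate a case with 5% power from one with 88%. Confidence is moderate that the look was distinct from the defined week 12 analysis. Its effect on the error rate ranges from none to about 8.5% against a nominal 5% (4.4% against 2.5%), and only the missing record can say where in that range the trial lies. The figures rest on two one-sided t tests, a 1 g/dl margin, assumed SDs, all 43 patients analysed, no gain from ANCOVA, and the hemoglobin criterion alone.

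**What to change.** - **SAP 5, power.** State that the 80% applied to 120 patients, that 43 were enrolled (23 and 20), and that 80% power is not claimed at this size. Give the planning SD and true difference if they were recorded, and otherwise say that they were not documented. Do not back-fill an SD.
- **SAP 5, adequacy.** Delete the statement on statistical validity. Say that precision will be judged by the achieved CI half-width against the 1 g/dl margin, reported with the per-protocol counts in each group.
- **SAP 3.2.4 and 8.1.** Put non-equivalence under H0, state the CI level, and declare the hemoglobin part of equivalence only if that CI lies within ±1 g/dl.
- **SAP 6.4.** Record the date of the look (before or after 23 March 2021), the number of patients, the data seen (pooled or by arm), who saw it, its role in ending recruitment, and whether it is the protocol 16.4 analysis. If by-arm results informed the stop, add a sensitivity CI adjusted for the look, with the assumed alternative total stated. Otherwise justify making no adjustment.

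Cost: wording only, no extra patients. The power statement becomes less favourable. With an equal-boundary (Pocock-type) two-stage adjustment, the sensitivity CI half-width grows by a factor of 1.16 (90% CI) or 1.13 (95% CI) if the alternative total was 120, and by 1.12 or 1.09 if it was 60.

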6.1 Timing of Analyses

The final analysis will be performed after the last study patient completes the week 24 visit and the database is clean. This analysis will produce all the safety results, including immunogenicity, at week 24.

6.2 Analysis Populations

6.2.1 Per Protocol Population

- All subjects who received any study drug and who completed at least week 12 follow up visit to evaluate primary efficacy endpoint and who did not substantially deviate from the protocol.

6.2.2 Safety Population

- All subjects who received any study treatment

6.3 Missing Data

Para los datos faltantes de hemoglobina se utilizará el método de la última observación llevada hacia adelante (LOCF).

6.4 Interim Analyses

A first interim analysis will be performed after the last study patient completes the week 12 visit and the database is clean. This analysis will produce all the efficacy and safety results at week 12.

7 Summary of Study Data

All data will be listed, taking into account site, subject, treatment, and visit number. All summary tables will be structured with a column for each treatment and will be annotated with the total population size relevant to that table, including any missing observations

Descriptive statistics:

Continuous variables will be summarized using descriptive statistics: N, mean, standard deviation, median, minimum and maximum.

Categorical variables will be presented using frequencies and percentages

Inferential statistics

Inferential statistics will be performed through intergroup analysis using ANCOVA covariance analysis comparing each treatment group (patients treated with HEMAX PFS versus those treated with EPREX/ ERYPO®) or the statistical “t” Student test for independent samples considering 5% significance level can be used. An additional intragroup analysis evaluating the variations in hemoglobin (increase from baseline to the average of the visits between weeks 8 and 12) adjusted for the baseline value, using a significance level of 5% will be calculated.

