16.5 EFFICACY ANALYSIS

The efficacy analysis will be performed for both FAS and PP populations. Descriptive statistics and inferential statistics will be performed through intergroup analysis (ANCOVA covariance analysis)-comparing each treatment group (patients treated with HEMAX PFS versus those treated with EPREX/ERYPO®) and an additional intragroup analysis analyzing the variations in hemoglobin (increase from baseline to the average of the visits between weeks 8 and 12) adjusted for the baseline value, using a significance level of 5%. Statistical analysis will be performed with SPSS software or equivalent.

The following parameters will be evaluated for treatment efficacy, according to the objectives defined by the protocol.

The **primary efficacy assessment** will be carried out through the levels of hemoglobin increase from baseline value to the mean value of the visits between week 8 and 12, comparing patients treated with HEMAX PFS versus those treated with EPREX/ERYPO®.

Additionally, **treatment equivalence** will be established if the difference between the two groups excludes a difference between treatment groups greater than 1g/ dl in hemoglobin increase from baseline value to the mean value of the visits between week 8 and 12 with a difference in the mean dose of epoetin alfa in these visits no greater than 20%.

The **secondary efficacy assessment** will be carried out through the evaluation of the following objectives:

- Percentage of responder patients (increase of Hb \geq 1g/ dl) after 12 weeks of treatment, comparing patients treated with HEMAX PFS versus those treated with EPREX/ERYPO®.

- Percentage of transfusion requirement after 12 weeks of treatment, comparing patients treated with HEMAX PFS versus those treated with EPREX/ ERYPO®.
- Intragroup efficacy (HEMAX PFS and EPREX/ ERYPO®) of treatment with Epoetin Alfa through increased levels of hemoglobin from baseline in each one of the intermediate visits until the week 12 visit.
- Evaluate the intragroup efficacy (HEMAX PFS and EPREX/ ERYPO®) of the change from the twice - a - week dosing during the titration phase to a weekly dosing during the maintenance phase through the variation of the hemoglobin levels from week 12 to the weeks 16, 20 and 24.

For **missing hemoglobin data**, the last observation carried forward method will be used.

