7.6 Treatment Compliance

The patients should return to the center all the containers with the drug product used during the study, and all the medications that they had not used during the study. The staff in the center recorded in the source document and on the patient accountability individual record, the patient number, and the number of returned containers.

During the study, the monitor checked continuously all the containers with the study medication (used, and non-used containers), and the corresponding accountability forms. At the same time, at each visit the card in which the patient recorded the date and drug product dose administered, is checked. Accountability records of the drug products used during the study were kept in the centers all the time. At the moment the study was ended a final accountability was carried out and all the remnant medication was withdrawn for destruction, as stated in current regulations. .

The following measures will de obtained related to treatment compliance:

- Epoetin dose (IU) administered every week in each group (mean \pm SD): Mean for cumulative doses per patient at the titration stage, maintenance stage, and during the whole treatment
- Number of patients that suspended the treatment at each visit

8 Efficacy Analyses

All efficacy variables will be listed by subject within study site. Data will be summarized by treatment group. Number and percentage will summarize categorical efficacy variables and Number, Mean, Standard Deviation, Minimum and Maximum will summarize continuous efficacy variables, whereas.

Inferential statistics will be performed through intergroup analysis analysis using ANCOVA covariance analysis comparing each treatment group (patients treated with HEMAX PFS versus those treated with EPREX/ ERYPO®) or the statistical “t” Student test for independent samples considering 5% significance level.

An additional intragroup analysis evaluating the variations in hemoglobin (increase from baseline to the average of the visits between weeks 8 and 12) adjusted for the baseline value, using a significance level of 5% will be performed

The assumptions regarding normality and homogeneity will be checked.

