8.1 Primary Efficacy Analysis

The primary efficacy analysis will be performed for Per Protocol population.

The primary efficacy assessment will be carried out through the levels of hemoglobin increase from baseline value to the mean value of the visits between week 8 and 12, comparing patients treated with HEMAX PFS versus those treated with EPREX/ ERYPO®.

Additionally, treatment equivalence will be established if the difference between the two groups excludes a difference between treatment groups greater than 1g/ dl in hemoglobin increase from baseline value to the mean value of the visits between week 8 and 12 with a difference in the mean dose of epoetin alfa in these visits no greater than 20%.

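### The SAP lets the primary between-arm comparison be made by ANCOVA or by an unadjusted t-test, gives no rule for choosing, and names no covariate for the ANCOVA

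*SAP*

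**What the plan says.** **SAP section 7 (inferential statistics)** gives ANCOVA for the between-arm comparison and then adds that the "Student test for independent samples considering 5% significance level can be used".

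**SAP section 8** repeats the pair, again ending in the "Student test for independent samples considering 5% significance level", with no condition attached to either method. It adds: "The assumptions regarding normality and homogeneity will be checked". Nothing follows from the result of that check.

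**SAP section 8.1** opens with "The primary efficacy analysis will be performed for Per Protocol population". It then gives the endpoint, the 1 g/dL margin and the 20% dose condition, but no model, covariate or confidence interval.

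**Baseline adjustment** appears in the SAP only in a separate sentence about an additional within-arm analysis (sections 7 and 8).

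**Protocol 16.5** says that "inferential statistics will be performed through intergroup analysis (ANCOVA covariance analysis") and offers no t-test. Its baseline-adjustment phrase closes the same long sentence, after the within-arm clause, so it can be read as covering the ANCOVA too.

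**Randomisation** was "stratified by gender, and in blocks per center" (SAP 4.3). Sex enters no analysis model.

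**Error level:** "The following equivalence statistical hypotheses is to be tested at a two-sided significance level of 5"% (SAP 3.2.4).

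**The concern.** An independent-samples t-test on the change in haemoglobin and an ANCOVA with baseline as covariate give different estimates and different standard errors. When both are allowed and no rule picks one, the plan does not fix the primary result.

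The circumstances make this matter more than usual. The trial is open-label (Protocol 13.2). SAP section 5 reports that "The interim analysis according to the obtained data showed, preliminary, that the results were those expected" and that recruitment stopped at 43 of the planned 120 patients. Equivalence on the primary endpoint also opens the way to secondary testing (SAP 3.2.4). Nothing in the documents shows that a method was chosen on results, but nothing in the plan prevents it.

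Two harms are possible: lost precision if the t-test is used, and more false equivalence if whichever test passes is reported. Each test used alone keeps its own error rate.

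**Working it through.** **Inputs from the documents.** Margin 1 g/dL; 23 and 20 patients enrolled (SAP section 5), with the per-protocol number possibly smaller; level 5% two-sided (SAP 3.2.4). The documents do not say whether this means 2.5% or 5% per side of the equivalence test, so both are shown.

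**Inputs assumed.** Neither document gives an SD or a baseline/follow-up correlation ρ. The main case takes baseline SD 0.75 and follow-up SD 1.0 g/dL; a second takes 0.7 and 1.2.

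**The plan's own figure.** The 60 per arm cannot be reproduced without an SD. Back-solving two one-sided tests at true difference 0, n per arm = 2·(SD·(z₁₋α + z₀.₉₀)/1)², gives:
- 2.5% per side: SD = √30/(1.960 + 1.282) = 1.69
- 5% per side: SD = √30/(1.645 + 1.282) = 1.87

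**Why the methods differ.** The t-test works with the SD of change, √(SDb² + SDf² − 2ρ·SDb·SDf). ANCOVA works with the residual SD, SDf·√(1 − ρ²). The t-test estimate keeps a share 1 − ρ·SDf/SDb of any chance baseline imbalance. Equivalence on haemoglobin is concluded if |estimate| + t₁₋α·SE < 1. For SDs 0.75/1.0:

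| ρ | SD of change | Residual SD | Imbalance kept by t-test |
|---|---|---|---|
| 0 | 1.25 | 1.00 | 100% |
| 0.2 | 1.12 | 0.98 | 73% |
| 0.4 | 0.98 | 0.92 | 47% |
| 0.6 | 0.81 | 0.80 | 20% |

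**Power and disagreement at true difference 0.** Simulated bivariate normal data, 40,000 trials per setting, 23 and 20 patients, SDs 0.75/1.0:

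| ρ | t-test vs ANCOVA, 5% per side | Verdicts differ | t-test vs ANCOVA, 2.5% per side | Verdicts differ |
|---|---|---|---|---|
| 0 | 65% vs 87% | 27% | 45% vs 77% | 38% |
| 0.2 | 78% vs 89% | 15% | 62% vs 79% | 23% |
| 0.4 | 90% vs 93% | 6% | 81% vs 86% | 10% |
| 0.6 | 98% vs 98% | 1% | 95% vs 95% | 2% |

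Other settings at 5% per side, ρ = 0/0.2/0.4/0.6:
- 18 and 16 patients, SDs 0.75/1.0: 47/63/79/94% (t-test) vs 75/77/84/94% (ANCOVA).
- 23 and 20 patients, SDs 0.7/1.2: 50/63/78/91% vs 68/71/79/90%. At ρ = 0.6 both SDs are 0.96, so there is nothing to gain and one degree of freedom is spent.

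**False equivalence at true difference 1 g/dL** (100,000 trials, 23 and 20 patients, both SD pairs, ρ from 0 to 0.8). Each test alone gives 4.9 to 5.1% at nominal 5% and 2.1 to 2.6% at nominal 2.5%. Reporting whichever passes gives about 5.5 to 7.6% and 2.8 to 3.9%.

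**Larger SD, near the back-solved value** (0.75/1.6, ρ 0 to 0.2; SD of change 1.77 to 1.63). Whichever-passes gives about 5.3% at nominal 5% and 1.2 to 1.6% at nominal 2.5%. The two tests still disagree in about 7 to 20% of trials at true difference 0.

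**Sex.** Adding sex multiplies the SE by about 1.00, 0.97 or 0.95 if sex explains 0, 5 or 10% of the residual variance.

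**The case against.** **The size is assumption-bound.** This stands. The gain from ANCOVA is about nil at ρ = 0.6, and from ρ = 0.4 with SDs 0.7/1.2. At the SD implied by the planned sample size, the error inflation nearly vanishes at 5% per side and is absent at 2.5%. That implied SD may itself be conservative, and the methods still disagree there.

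**Only half of the equivalence rule is modelled.** Also true. Equivalence further requires a mean-dose difference of no more than 20% (SAP 3.2.4 and 8.1). The percentages describe the haemoglobin criterion alone and are upper bounds on declaring equivalence overall.

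**Baseline haemoglobin is implied.** ANCOVA needs a covariate, and Protocol 16.5 mentions only this one. That is a fair reading of the Protocol, but its wording is ambiguous, and the SAP moves the phrase into a separate within-arm sentence. It does not explain the added t-test in any case, and the SAP's summary of changes does not list one.

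**The assumption check could select the method.** The SAP does not say so. It could hardly serve, since both methods assume normal errors with equal variance.

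**Adding sex now is itself a late choice.** Sex is not in Protocol 16.5, and omitting it costs little or no precision. But adjusting for the randomisation stratum is standard practice, and the factor was fixed before any data existed.

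**Conclusion.** The concern holds. The text leaves the primary comparison open between two methods, without a selection rule and without a stated covariate, and it is looser than the Protocol. That part needs no assumption.

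The consequence ranges from negligible to material, depending on SDs and a correlation that the documents do not give. In the main case at 23 and 20 patients, the t-test costs up to 22 percentage points of power at 5% per side (87 − 65) and 32 at 2.5% (77 − 45), and nothing at ρ = 0.6. Inflation of false equivalence is modest: at most about 2.6 points above a nominal 5% (7.6 − 5.0) and 1.4 above 2.5% (3.9 − 2.5). This should be corrected. It does not invalidate either test when used alone, and no results-driven choice is shown.

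**What to change.** In SAP sections 7, 8 and 8.1, replace the either/or wording with one primary analysis: ANCOVA of the haemoglobin increase from baseline to the mean of the week 8 to 12 visits, with treatment, baseline haemoglobin and sex as terms, and the confidence interval for the adjusted treatment difference judged against ±1 g/dL. State the interval's coverage so that it matches the level in SAP 3.2.4. The 20% dose condition stays as it is.

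Keep any t-test only as a labelled sensitivity analysis that cannot change the equivalence conclusion. Leave site out of the model, because many centres enrolled one patient or none (SAP section 5).

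If the analysis has already been run, report the ANCOVA as primary, since it is the method the Protocol names, and disclose both results.

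Cost: one sentence in each of three places and two degrees of freedom (baseline haemoglobin and sex). No new data are needed, since both variables are already collected.
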